**DOCUMENT HISTORY**

Document	Date of Issue	Summary of Change
Revised Protocol 06	14-Oct-2020	The primary purpose of Revised Protocol 06 is to extend the collection of Overall Survival (OS) data for approximately 5 additional years. In addition, data associated with the primary, secondary, and exploratory efficacy outcomes (eg, melanoma recurrence data, data on development of new primary melanomas and non-melanoma cancers, subsequent anti-cancer therapies) will continue to be collected on Case Report Forms. Study drug-related serious adverse events (SAEs) will continue to be collected, whereas follow-up surveillance imaging assessments, plasma biomarker samples, and the EQ-5D questionnaire will no longer be required during extended follow-up.
Administrative Letter 03	15-Feb-2019	The purpose of this administrative letter is to change the Study Director for this study.
Administrative Letter 02	19-Dec-2017	The purpose of this administrative letter is to confirm that a surveillance assessment is required at the month 24 time point (relative to the first dose of study treatment).
Revised Protocol 05	26-Jan-2017	Incorporates Amendment(s) 18
Amendment 18	26-Jan-2017	The main purpose of this global amendment is to: 
 
• Add an interim analysis of RFS after all subjects have a minimum of 18 months of follow-up (approximately 350 RFS events are anticipated at this analysis).
 
• Change the name and coordinates of the new Medical Monitor
 
• Add the Mechanism for Action for Ipilimumab
 
• Confirm that also blood samples from subjects receiving Ipilimumab will also be evaluated for development of Anti-Drug Antibody (ADA).
 

Revised Protocol 04	04-Aug-2016	Incorporates Amendment(s) 17
Amendment 17	04-Aug-2016	The main purpose of this global amendment is to: 
 
• Addition of Adrenocorticotrophic hormone (ACTH) test at Week 45 in subjects receiving ipilimumab/ipilimumab-placebo at Week 48 (Note: All subjects will have completed 36 weeks of treatment prior to implementation of this amendment.)
 
• Clarify that the minimum time between dosing visits is 12 days between Nivolumab administrations
 
• Add information on surveillance scan requirements in case the patient discontinues and starts new systemic therapy.
 
• Update the contraception section
 
• Updates in the treatment algorithms
 

Revised Protocol 03	24-Feb-2016	Incorporates Amendment(s) 16

Document	Date of Issue	Summary of Change
Amendment 16	24-Feb-2016	The main purpose of this global amendment is to: 
 
1) Increase the visit window from <math>\pm 2</math> days to <math>\pm 3</math> days for all dosing visits, except for Week 24, Week 36 and Week 48 where the visit window will increase from <math>\pm 2</math> days to <math>\pm 7</math> days.
 
2) Clarify that the minimum time between dosing visits is 12 days
 
3) Revise and clarify the Prohibited and /or Restricted Treatments
 
4) Update the acceptable methods of contraception
 

Revised Protocol 02	06-Aug-2015	Incorporates Amendment(s) 15
Amendment 15	06-Aug-2015	The main purpose of this global amendment is to: 
 
1) Incorporate the definition of immune-mediated adverse events
 
2) Incorporate the Adverse Event Management Algorithms for Immuno-oncology Agents as an appendix, and updated terminology to be consistent throughout document
 
3) Clarify that follow-up of laboratory toxicities will continue until toxicities resolve, return to baseline, or are deemed irreversible based on on-site/local laboratory results.
 
4) Clarify that follow-up of immune-mediated adverse drug reactions will continue until toxicities resolve, return to baseline, or are deemed irreversible
 
5) Revise the discontinuation criteria to be consistent with the Nivolumab USPI
 
6) Revise the definition of recurrence free survival to include new primary melanoma
 
7) Add censoring rules for primary analysis of recurrence free survival
 
8) Clarify that subjects will continue to be followed for recurrences (until local or regional recurrences for all subjects and until distant recurrence for Stage III subjects) and survival
 

Revised Protocol 01	02-Apr-2015	Incorporates Amendment(s) 09 and Administrative Letter 01

Document	Date of Issue	Summary of Change
Amendment 09	02-Apr-2015	
 
1) The main purpose of this global amendment is to clarify the age requirement to participate in the study as the inclusion of adolescents may not be appropriate per local regulations.
 
2) Additional clarifications have been made to other inclusion/exclusion criteria.
 
3) There is also a new requirement regarding additional sample collection (serum, and biopsy of affected organ) for biomarker analysis. This collection will be done upon occurrence of <math>\geq</math> Grade 3 drug-related AE and lab abnormalities regarded as a drug related SAE when clinically safe and feasible
 
4) This amendment will also be used to implement recent changes in the program level protocol template as well as changes to the standard protocol model document
 
5) This amendment applies to all subjects
 

Administrative Letter 01	21-Jan-2015	
 
1) IND Number 115,195
 
2) The title of Section 3.3.1, Item 2 should read “Target Population”
 
3) First survival follow-up visit will take place 3 months after Follow-up 2
 

Original Protocol	11-Nov-2014	Not applicable

## SYNOPSIS

### Clinical Protocol CA209238

**Protocol Title:** A Phase 3, Randomized, Double-blind Study of Adjuvant Immunotherapy with Nivolumab versus Ipilimumab after Complete Resection of Stage IIIb/c or Stage IV Melanoma in Subjects who are at High Risk for Recurrence.

(CheckMate 238: CHECKpoint pathway and nivoluMAb clinical Trial Evaluation 238)

**Investigational Product(s), Dose and Mode of Administration, Duration of Treatment with Investigational Product(s):**

Ipilimumab 10 mg/kg/dose IV q3 weeks x 4 doses, then 10 mg/kg/dose IV q12 weeks starting at week 24 or

Nivolumab 3 mg/kg/dose IV q2 weeks

Treat subjects until disease recurrence, unacceptable toxicity or subject withdrawal of consent, with a maximum of 1 year of treatment.

**Study Phase:** 3

**Research Hypothesis:** Treatment with nivolumab will improve recurrence-free survival as compared to ipilimumab in subjects with completely resected Stage IIIb/c or Stage IV no evidence of disease (NED) melanoma who are at high risk for recurrence.

**Objectives:**

**Primary:**

- To compare the efficacy, as measured by recurrence free survival (RFS), provided by nivolumab versus ipilimumab in subjects with completely resected Stage IIIb/c or Stage IV NED melanoma who are at high-risk for recurrence.

[figure not shown]
**Secondary:**

- To compare the overall survival of nivolumab vs ipilimumab in subjects with completely resected Stage IIIb/c or Stage IV NED melanoma who are at high risk for recurrence;
- To assess the overall safety and tolerability of nivolumab and ipilimumab in subjects with completely resected Stage IIIb/c or Stage IV NED melanoma who are at high risk for recurrence;
- To evaluate whether PD-L1 expression is a predictive biomarker for RFS;
- To evaluate the Health Related Quality of Life (HRQoL) as assessed by European Organisation for Research and Treatment of Cancer (EORTC) QLQ-C30.

[REDACTED]

[REDACTED]

**Study Design:**

For both arms, the treatment duration is maximum one year.

This is a Phase 3, randomized, double-blinded study of nivolumab versus ipilimumab in subjects (≥ 15 years) with complete resection Stage IIIb/c or Stage IV NED melanoma at high risk for recurrence.

Approximately 800 subjects will be randomized 1:1 and stratified by PD-L1 status (positive vs negative/indeterminate) and American Joint Committee on Cancer (AJCC) stage.

Dose reductions will not be allowed.

Subjects will be treated with one of the following:

Arm A: ipilimumab: 10 mg/kg IV q3 weeks for 4 doses, then q12 weeks starting at Week 24 with nivolumab placebo IV q2 weeks

Arm B: nivolumab 3mg/kg IV q2 weeks with ipilimumab placebo IV q3weeks for 4 doses, then q12 weeks starting at Week 24

All subjects will be treated until recurrence of disease, unacceptable toxicity, or subject withdrawal of consent with a maximum of 1 year of treatment.

Note: As of Dec-2016, all subjects in both treatment groups were off study treatment.

**Study Population:** High risk, completely resected Stage IIIb/c and IV melanoma subjects.

Key Inclusion Criteria:

- At least 15 years of age
- Except: where local regulations and/or institutional policies do not allow for subjects < 18 years of age (pediatric population) to participate. For those sites, the eligible subject population is ≥ 18 years of age.
- All subjects must be either Stage IIIb/c or Stage IV AJCC (7th edition) and have histologically confirmed melanoma that is completely surgically resected in order to be eligible. Subjects must have been surgically rendered free of disease with negative margins on resected specimens. Please refer to [Appendix 1](#) for description of AJCC 7th editions of TNM and staging.
- If Stage III melanoma (whether Stage IIIb or IIIc) the subjects usually have clinically detectable lymph nodes that are confirmed as malignant on the pathology report and/or ulcerated primary lesions. Subjects who are “N2c” classification with 2-3 metastatic nodes and in transit metastases/satellites without metastatic nodes, or, “N3” classification with any “T” and 4+ metastatic nodes, or matted nodes, or in transit metastases/satellites with metastatic nodes are eligible. The pathology report for both Stage IIIb and IIIc must be reviewed, signed and dated by the investigator; this process will be confirmed during the IVRS randomization call. Clinically detectable lymph nodes are defined as:
  - 1) a palpable node (confirmed as malignant by pathology)

- 2) a non-palpable but enlarged lymph node by CT scan (at least 15 mm in short axis) and confirmed as malignant by pathology
- 3) a PET scan positive lymph node of any size confirmed by pathology
- 4) evidence of pathologically macrometastatic disease in one or more lymph nodes defined by one or more foci of melanoma at least 1cm in diameter

If Stage IV melanoma, the pathology report confirming negative margins must be reviewed, dated, and signed by the investigator prior to randomization.

- Complete resection of Stage III disease that is documented on the surgical and pathology reports or complete resection of Stage IV disease with margins negative for disease that is documented on the pathology report.
- Complete resection must be performed within 12 weeks prior to randomization
- All subjects must have disease-free status documented by a complete physical examination and imaging studies within 4 weeks prior to randomization. Imaging studies must include a CT scan of the neck, chest, abdomen, pelvis and all known sites of resected disease in the setting of Stage IIIb/c or Stage IV disease, and brain magnetic resonance (MRI) or CT (brain CT allowable if MRI is contraindicated or if there is no known history of resected brain lesions).
- Tumor tissue from the resected site of disease must be provided for biomarker analyses. In order to be randomized, a subject must have a PD-L1 expression classification (positive, negative/or indeterminate) as determined by a central lab.

Key Exclusion Criteria:

- History of ocular/uveal melanoma
- Subjects with active, known, or suspected autoimmune disease. Subjects with type I diabetes mellitus, residual hypothyroidism due to autoimmune thyroiditis only requiring hormone replacement, skin disorders (such as vitiligo, psoriasis, or alopecia) not requiring systemic treatment are permitted to enroll.
- Subjects with previous non-melanoma malignancies are excluded unless a complete remission was achieved at least 3 years prior to study entry and no additional therapy is required or anticipated to be required during the study period (exceptions include but are not limited to, non-melanoma skin cancers; in situ bladder cancer, in situ gastric cancer, in situ colon cancers; in situ cervical cancers/dysplasia; or breast carcinoma in situ)
- Subjects with a condition requiring systemic treatment with either corticosteroids ( $\geq 10$  mg daily prednisone or equivalent) or other immunosuppressive medications within 14 days of study drug administration. Inhaled or topical steroids are permitted in the absence of active autoimmune disease.
- Prior therapy for melanoma except surgery for the melanoma lesion(s) and/or except for adjuvant radiation therapy (RT) after neurosurgical resection for central nervous system (CNS) lesions and except for prior adjuvant interferon (see qualifier below). Specifically subjects who received prior therapy with interferon, anti-PD-1, anti-PD-L1, anti-PD-L2, anti-CD137, or anti-CTLA-4 antibody (including ipilimumab or any other antibody or drug specifically targeting T cell co-stimulation or checkpoint pathways) are not eligible.
  - i) Prior treatment with adjuvant interferon is allowed if completed  $\geq 6$  months prior to randomization.

**Study Drug:** includes both Investigational [Medicinal] Products (IP/IMP) and Non-investigational [Medicinal] Products (Non-IP/Non-IMP) as listed:

Study Drug for CA209238		
Medication	Potency	IP/Non-IP
BMS-936558-01 (Nivolumab) Solution for Injection	100 mg (10 mg/mL)	IP
Ipilimumab Solution for Injection	200 mg (5 mg/mL)	IP
0.9% Sodium Chloride for Injection	N/A	IP
5% Dextrose for Injection	N/A	IP

**Study Assessments:** Recurrence-free survival is the primary endpoint of the trial. It is defined as the date between the date of randomization and the date of first recurrence (local, regional or distant metastasis), new primary melanoma, or death (whatever the cause), whichever occurs first. Subjects will be assessed for recurrence (until local, regional, or distant recurrence (whichever comes first) for Stage IV subjects and until distant recurrence for Stage III subjects) by CT or MRI as follows:

- Screening.
- Treatment Period: Every 12 weeks ( $\pm 7$  days) from first dose of study drug through 12 months (relative to the first dose of study drug)
- Follow-up Period:
  - Every 12 weeks ( $\pm 7$  days) through 12 months for subjects who discontinued early from treatment (relative to the first dose of study drug)
  - Every 12 weeks ( $\pm 14$  days) if  $> 12$  months through 24 months (relative to the first dose of study drug)
  - Every 6 months ( $\pm 4$  weeks) if  $> 24$  months through and up to Year 5 (relative to the first dose of study drug). Although surveillance assessments will not be conducted beyond Year 5, data on recurrence of melanoma (loco-regional and distant), as well as development of new primary melanomas and non-melanoma cancers will continue to be collected in the respective Case Report Forms for an additional 5 years, for a total study duration of approximately 10 years.

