### **8.1 Sample Size Determination**

The sample size is calculated to compare RFS between subjects randomized to receive nivolumab vs ipilimumab. RFS will be evaluated for a treatment effect at an overall alpha level of 0.05 (two-sided) with approximately 85% power. The number of events and power were calculated assuming a delayed treatment effect and cure fraction.

Approximately 900 subjects have been randomized to the two treatment arms in a 1:1 ratio. Based on current accrual and revised piece-wise accrual rate assumptions, accrual duration was 7.5 months. Taking into account the actual AJCC disease stage distribution, slower event rate, higher cure rates, and some early drop-out, the original planned 507 events might not be reached by the final RFS analysis (ie, after all subjects have a minimum of 36 months of follow-up). Approximately 450 RFS events are anticipated at the final RFS analysis, ensuring at least 85% power to detect a hazard ratio of 0.75 (critical hazard ratio of 0.83) with an overall type I error of 0.05 (two-sided). Sample size calculations for this study design were done using EAST 6 (v 6.3.1) and R.

An interim analysis of RFS will take place after all subjects have a minimum of 18 months of follow-up. Approximately 350 RFS events are anticipated at this analysis. The stopping boundary at the interim analysis will be derived based on the exact number of RFS events at interim using Lan-DeMets alpha spending function with O'Brien-Fleming boundaries. With an interim RFS analysis at 350 RFS events (about 78% information fraction), the critical hazard ratio would be 0.78 and the type I error would be 0.022 (two-sided). The type I error to be used for final RFS analysis would be 0.043 (two-sided).

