#### **8.4.2.2 Secondary Endpoint Methods**

The secondary OS analysis will be conducted using a two-sided log-rank test stratified by PD-L1 status and Stage at screening in randomized subjects. The hazard ratio and corresponding two-sided (1-adjusted  $\alpha$ )% CI will be estimated using a Cox proportional hazards model, with treatment arm as a single covariate, stratified by the above factors. OS curves, OS medians with 95% CIs and OS rates at 12 and 24 months with 95% CIs will be estimated using Kaplan-Meier methodology.

To evaluate PD-L1 expression as a predictive biomarker, a Cox proportional hazards model will be used to test the interaction between PD-L1 expression (positive vs negative) and treatment arm for the RFS endpoint. Additionally, RFS will be analyzed within each PD-L1 expression subgroup (positive and negative) including log-rank tests and hazard ratios with corresponding confidence intervals. RFS curves and medians will be estimated using Kaplan-Meier methodology. These analyses will be descriptive and not adjusted for multiplicity. Other exploratory analyses, such as associations between PD-L1 expression and other efficacy endpoints and evaluations of different thresholds for PD-L1 positivity, will also be planned in the SAP.

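### Protocol 8.4.2.2 does not state that the PD-L1 interaction and subgroup analyses of RFS are stratified by AJCC stage, a randomization factor; stating it would give a small, nearly free gain in precision

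*Protocol*

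**What the plan says.** The Synopsis (Study Design) states that subjects are randomized 1:1, "stratified by PD-L1 status (positive vs negative/indeterminate) and American Joint Committee on Cancer (AJCC) stage". Protocol 4.4 gives the three stage levels held in the IVRS: IIIb/c, IV M1a-M1b and IV M1c. The primary RFS test (Synopsis; Protocol 8.4.2.1; DMC SAP 6.5) and the OS test (Protocol 8.4.2.2; DMC SAP 6.7) are both stratified by PD-L1 status and stage.

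One secondary objective reads "To evaluate whether PD-L1 expression is a predictive biomarker for RFS". For it, the second paragraph of Protocol 8.4.2.2 says that "a Cox proportional hazards model will be used to test the interaction between PD-L1 expression (positive vs negative) and treatment arm" for RFS, and that "RFS will be analyzed within each PD-L1 expression subgroup (positive and negative) including log-rank tests and hazard ratios" with confidence intervals. Neither sentence names stage as a stratum or a covariate. The same paragraph adds Kaplan-Meier curves and medians and declares the analyses descriptive, without multiplicity adjustment. It leaves only other exploratory work (other endpoints, other PD-L1 thresholds) to the SAP.

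The SAP supplied is the one for the DMC. It lists the PD-L1 objective (3.2) but specifies no PD-L1 interaction or subgroup analysis. The opening of Protocol Section 8 mentions a separate SAP for the clinical study report, which was not supplied.

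**The concern.** In Section 8.4.2.2 the OS paragraph writes out both stratification factors, and the next paragraph writes out the PD-L1 methods with neither a stage stratum nor a stage term. A programmer who follows the text would fit these analyses without stage.

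The sponsor's own planning suggests that stage is prognostic. Protocol 8.1 lists the actual stage distribution among the reasons why the planned 507 events might not be reached. When a prognostic factor is left out of a Cox model, the hazard ratio for treatment moves toward 1. When the arms were also balanced on that factor by design, the unstratified standard error is somewhat too large and the test is conservative.

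The loss falls on the formal tests and estimates that serve a named secondary objective, where event numbers are already limited. The subgroup hazard ratios would also be read beside a primary hazard ratio that is conditional on stage, although they estimate a slightly different quantity.

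**Working it through.** **Inputs from the documents.** About 900 subjects, 1:1, 7.5 months of accrual, at least 36 months of follow-up, 450 events at final RFS analysis, HR 0.75, overall two-sided alpha 0.05 (Protocol 8.1). Stage III to Stage IV about 80/20 (DMC SAP 5).

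**Assumed, because the documents give no figure.** Stage hazard ratios from 1 to 4; a 14/6 split of the Stage IV subjects into M1a-M1b and M1c; PD-L1-positive share 35% or 60%, with everyone else negative; stage independent of PD-L1; exponential hazards (the protocol's delayed effect and cure fraction have no stated parameters); no dropout.

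**Step 1: the plan's own figures.** Power = Φ(|ln HR| × √d / 2 − z). With d = 450, HR 0.75 and z = 1.960: 0.2877 × 21.213 / 2 − 1.960 = 1.091, so power is 86.2%. At the final-look alpha of 0.043 it is 84.8%, and for the two-look design 85.6%. The plan states at least 85%. The critical HR, exp(−2z/√450), is 0.831 at alpha 0.05 and 0.826 at 0.043 (stated 0.83). At 350/450 = 78% information, Lan-DeMets O'Brien-Fleming spending gives interim alpha 0.0221, critical HR 0.783 and final nominal alpha 0.0435. The plan states 0.022, 0.78 and 0.043. All agree within rounding. The plan states no power for the PD-L1 analyses.

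**Step 2: power in a PD-L1 subgroup before stage is considered.** The same formula at HR 0.75 and alpha 0.05, for a subgroup holding 35%, 50% or 65% of the 450 events (about 157, 225 or 292), gives 44%, 58% and 69%.

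**Step 3: effect of leaving stage out.** Simulation, 3000 runs per scenario: 900 subjects, 1:1 allocation blocked within PD-L1 by stage, follow-up of 36 to 43.5 months, hazards calibrated to 450 expected events. Each data set was analyzed without stage and stratified by stage. The interaction was a Wald test on the difference between the two subgroup log hazard ratios. Subgroup columns use a true HR of 0.75 in both subgroups and give the range over both subgroups and both PD-L1 shares. Interaction columns use true HRs of 0.60 (positive) and 0.90 (negative), a true ratio of 0.60/0.90 = 0.667, and give the 35% share and then the 60% share. Arrows run from unstratified to stratified.

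| Hazard, III / M1a-M1b / M1c | Subgroup power gained (points) | Subgroup HR | Interaction power (%) | Ratio of HRs |
|---|---|---|---|---|
| 1 / 1 / 1 | −0.4 to 0.2 | 0.747–0.749 → 0.747–0.749 | 51.5 → 51.1; 55.8 → 56.0 | 0.665 → 0.665; 0.668 → 0.668 |
| 1 / 1.5 / 1.5 | −0.2 to 0.4 | 0.746–0.752 → 0.745–0.751 | 51.5 → 52.0; 54.0 → 54.9 | 0.666 → 0.664; 0.670 → 0.667 |
| 1 / 2 / 2 | 1.4 to 1.8 | 0.750–0.756 → 0.746–0.751 | 49.6 → 51.5; 54.0 → 55.9 | 0.668 → 0.662; 0.674 → 0.666 |
| 1 / 2 / 3 | 2.0 to 2.7 | 0.755–0.757 → 0.748–0.750 | 47.4 → 49.7; 51.5 → 55.0 | 0.676 → 0.666; 0.678 → 0.666 |
| 1 / 3 / 4 | 4.9 to 6.1 | 0.762–0.767 → 0.747–0.750 | 44.9 → 51.4; 47.9 → 54.5 | 0.686 → 0.663; 0.696 → 0.671 |

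The first row, where stage has no effect, shows noise of up to 0.4 point, so the 1.5-times row shows no clear subgroup change. Up to 1/2/3 the subgroup HR moves by at most 0.007 when the truth is 0.75. In the PD-L1-positive subgroup with a true HR of 0.60 it moves by about 0.01 (0.609 → 0.599 and 0.610 → 0.599).

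**Step 4: validity.** With HR 0.75 in both subgroups there is no interaction, and a 5% test should reject 5% of the time. At 1/2/3 the unstratified test rejects 4.1% and 3.9%, the stratified test 4.6% and 4.8%. At 1/3/4 the figures are 3.8% and 3.9% against 5.3% and 5.7%. The Monte Carlo standard error is √(0.05 × 0.95 / 3000) = 0.4 point. The unstratified interaction test therefore errs on the conservative side.

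**The case against.** The case against raising this is substantial, and much of it stands.

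- **Descriptive status.** Section 8.4.2.2 declares the analyses descriptive. No alpha, hierarchical step or decision rule depends on them, and the formally tested endpoints are stratified by stage. This stands and limits the importance of the point.
- **Silence.** A reader might infer that the plan chose to ignore stage. The text does not say unstratified, and the SAP for the clinical study report may well add stage, so that inference goes beyond the documents. What remains is that 8.4.2.2 itself defines these tests and leaves only other exploratory work to the SAP, so the protocol's stated method is incomplete.
- **Choice of estimand.** A reader might also infer that unstratified results would be biased or invalid. They would not: a hazard ratio averaged over stage is a legitimate quantity, and the unstratified test after stratified randomization is valid, if slightly conservative. The movement toward 1 matters for comparability with the primary hazard ratio.
- **Other readouts.** Kaplan-Meier curves and medians by PD-L1 subgroup are planned as well, so the tests and hazard ratios are not the only evidence on the objective.
- **Timing.** The opening of Section 8 says that all planned analyses were run on the January 2020 lock, so an edit now changes none of them. The same paragraph keeps exploratory analyses going with similar methods, and there the clarification still has use.
- **Size.** Low event numbers cost far more than the missing stratum: power is 44% at HR 0.75 if a subgroup holds 35% of events.

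**Conclusion.** The point holds as a minor gap in specification. Protocol 8.4.2.2 does not state that the PD-L1 interaction model and the subgroup tests and hazard ratios are stratified by stage, although stage is a randomization factor and a stratum of the primary RFS and OS analyses. Run as written, they lose a little precision and are not on the same stage-conditional scale as the primary hazard ratio.

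For assumed Stage IV hazards of 1.5 times up to 2 and 3 times that of Stage III, the cost is about 0 to 3.5 power points and about 0.01 or less on the subgroup hazard ratio. It reaches about 5 to 6.6 points, and up to about 0.02 on a true hazard ratio of 0.75, only at an assumed 3 and 4 times. The direction is secure if stage is prognostic. The size rests on the assumptions listed in the working, chiefly the stage hazard ratios. The primary RFS conclusion, the OS test and the type I error are untouched.

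**What to change.** In Protocol 8.4.2.2, and in the specification of the exploratory analyses that continue under the opening paragraph of Section 8, state two things. First, the interaction Cox model contains treatment, PD-L1 and treatment-by-PD-L1 and is stratified by AJCC stage as randomized per IVRS (IIIb/c, IV M1a-M1b, IV M1c). Second, the log-rank tests and Cox hazard ratios within each PD-L1 subgroup are stratified by the same factor. If the SAP for the clinical study report already says so, only the protocol text needs to be aligned.

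The cost is about one sentence and one program option, since stage per IVRS is already summarized (DMC SAP 6.3.2). The only downside is that a small M1c stratum within a PD-L1 subgroup will add little information.
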